8.6.1.1 Responder Analysis

A responder analysis at each appropriate post-dose follow-up visit (see Table 1 and Table 2 for specific timings) will be conducted for the Norovirus G1.1 HBGA BT50. During active period, the numbers and percentages (with 95% CIs) of subjects with a ≥ 2 -, 3- or 4-fold increase from baseline antibody levels will be summarized, respectively. Durability of immune responses will be evaluated using the safety follow-up period samples collected at 6 months post the second dose (Month 7 for Cohort 1, Month 8 for Cohort 2, and Month 9 for Cohort 3). Numbers and percentages of subjects with a ≥ 2 -, 3- or 4-fold increase from baseline antibody levels at both 28 day post the second dose (Day 57 for Cohort 1, Day 85 for Cohort 2, and Day 113 for Cohort 3) and 6 month post the second dose will be summarized, where percentages will be calculated as of the number of subjects with a ≥ 2 -, 3- or 4-fold increase from baseline antibody levels at 28 day post the second dose will be summarized, where percentages will be calculated as of the number of subjects with a ≥ 2 -, 3- or 4-fold increase from baseline antibody levels at 28 day post the second dose. Fisher's exact test will be used to compare the percentages of responders for each category among cohorts.

8.6.1.2 Analysis of Covariance (ANCOVA)

To account for the potential differences in baseline antibody level, ANCOVA will be used to analyze and compare the immunogenicity endpoints at each post-dose visits conditioning on baseline values for the Norovirus G1.1 HBGA BT50 assay. Separate models will be estimated at each post-dose visit, using log titer as a dependent variable, treatment group as a factor and baseline log titer as a covariate. LSMs for each cohort and differences in LSM between cohorts will be estimated from each model along with 95% CIs. Both LSMs for each cohort and the differences in LSM between cohorts along with their 95% CIs will be exponentiated to the original scale, resulting geometric LSMs for each cohort and LS-GMR between cohorts. In order to compare immunogenicity assay results among treatment groups, significance on 28 days post the second dose, pairwise comparisons will be performed.

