3.2 Randomization and blinding

As VXA-NVV-105 is a Phase 1b, open-label, boost-optimization study to determine the immunogenicity, safety and tolerability of vaccine VXA-G1.1-NN at dose level 1×10^{10} IU ± 0.5 log with varying boosting schedules, neither randomization nor blinding will be applicable for this study. Both subjects and investigators will be aware of individual treatment assignment.

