4.0 Study Endpoints

- 4.1 **Primary endpoints**
 - Number of VP1 specific IgA antibody secreting cells (ASC) by enzyme-linked immunospot (ELISpot) by treatment group and visit
 - Geometric mean titer (GMT) and geometric mean fold rise (GMFR) over the initial GMT of Norovirus G1.1 histo-blood group antigen (HBGA) blocking antibodies (BT50) by treatment group and visit
 - Geometric mean (GM) and GMFR over the initial results of VP1 specific serum IgG by Meso Scale Discovery (MSD) by treatment group and visit

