4.2 Secondary endpoints

- Frequencies, durations, and severities of solicited symptoms of reactogenicity (local, systemic) for 1 week following each dose of study drug by treatment group
- Frequencies, durations, and severities of unsolicited AEs, SAEs, AESIs and NOCIs through each active study period (4 weeks post each vaccination) by treatment group
- Number and percentages of subjects with ≥2-, 3-, 4-fold increase over baseline titer of Norovirus G1.1 HBGA BT50 results by treatment group and visit
- Geometric Least Square Mean (LSM) of post-dose Norovirus G1.1 HBGA BT50 titer by treatment group and visit adjusted for baseline titer level
- Least Square Geometric Mean Ratio (LS-GMR) of post-dose titer Norovirus G1.1 HBGA BT50 between treatment groups by visit adjusted for baseline titer level

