7.0 Statistical Considerations and Analysis

7.1 Derived Variables

The below table provides the list of derived variables for demographic and baseline characteristics, various duration derivations, baseline derivation and other important derivations applicable for this study.

Table 4: Derived Variables

Variables	Formula			
Demographic and Baseline Characteristics				
Age at informed consent (in years)	Integer ((date of informed consent – date of birth + 1) / 365.25)			
Body Mass Index	Weight (kg) / height (m)²			
Derivation of Durations				
Study day at any visit	Date of interest – date of first dose of vaccine. One day is added if the difference is ≥ 0 .			
Duration of any events	End date of event – start date of event + 1			
Baseline Derivations				
Laboratory baseline	The baseline value is defined as the last observation prior to or on the date of the first dose of study drug.			
Change from baseline	Post baseline value – baseline			
Percent change from baseline	[(Post baseline value – baseline) / baseline] * 100			
Change from previous visit	Current value – previous value			
Percent change from previous visit	[(Current value – previous value) / previous value] * 100			
Other Derivations				
Geometric mean/geometric, mean titer/geometric mean concentration	Individual values will be transformed via the natural log, mean values along with 95% CIs will be calculated, which will be transformed back to the original scale via exponentiation.			
Geometric mean fold rise	The mean values and 95% CIs of the log ratio of post dose assay values relative to baseline will be calculated, then transformed back to the original scale via exponentiation.			
Geometric least square mean	Least square means and 95% CIs for each treatment group will be calculated from ANCOVA with immunogenicity assay result on log scale at post dose visit as a dependent variable, treatment group as a factor and baseline immunogenicity assay result on log scale as a covariate, which will be then transformed to the original scale via exponentiation.			
Least square geometric mean ratio	Least square mean differences and 95% CIs among treatment groups will be estimated from the abovementioned ANCOVA model, which will be then transformed to the original scale via exponentiation.			

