8.6.1 Analysis methods

Immunogenicity will be evaluated using cellular and humoral immune function assays from blood and mucosal (saliva and nasal swab) samples. Samples will be collected from all subjects according to the time points specified in the SoE.

Results of the following immunogenicity assay results will be summarized descriptively by treatment group and visit and will be reported in the final CSR. Specific endpoints are listed in Sections 4.1 and 4.3.

- VP1 specific IgA ASC by ELISpot
- Norovirus G1.1 HBGA BT50
- VP1 specific serum IgG by ELISA or MSD
- VP1 specific IgG ASC by ELISpot
- VP1 specific serum IgA by ELISA or MSD

Additional exploratory endpoints will be evaluated and reported outside the scope of this SAP.

Kolmogorov-Smirnov test will be used to examine the normality assumptions of the immunogenicity assay results in log scale for each treatment group. If normality assumptions are met for all treatment groups, pairwise comparisons will be performed between treatment groups using Student t-test; Wilcoxon rank sum test will be used if otherwise.

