8.6.2 Multiplicity

There will be multiple outcomes pertaining to immunogenicity; however, each outcome will be analyzed separately, and no corrections will be made to account for multiplicity. Pairwise comparisons among cohorts will also be conducted; Holm-Bonferroni method will be used to control family-wise error rate, both adjusted and unadjusted p-values will be reported.

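### Baseline-adjusted ANCOVA covers BT50 only; VP1 serum IgG, also primary, has no baseline-adjusted comparison between the non-randomised cohorts

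*SAP*

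**What the plan says.** VP1 serum IgG is one of three primary immunogenicity endpoints in Protocol section 3 and SAP 4.1. SAP 4.1 defines it as "Geometric mean (GM) and GMFR over the initial results of VP1 specific serum IgG by Meso Scale Discovery (MSD) by treatment group and visit". Table 4 in SAP 7.1 describes the fold rise as a summary: "The mean values and 95% CIs of the log ratio of post dose assay values relative to baseline will be calculated".

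SAP 8.6.1.2 introduces ANCOVA because cohorts may start from different antibody levels, and then confines it to one assay: "conditioning on baseline values for the Norovirus G1.1 HBGA BT50 assay". The endpoint list in SAP 4.2 agrees. Its adjusted between-cohort entry is the "Least Square Geometric Mean Ratio (LS-GMR) of post-dose titer Norovirus G1.1 HBGA BT50 between treatment groups by visit adjusted for baseline titer level", and IgG has no counterpart. Table 4 words the model for any assay ("ANCOVA with immunogenicity assay result on log scale at post dose visit as a dependent variable, treatment group as a factor", with the log baseline result as covariate), but no section assigns it to IgG.

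The between-cohort test that does reach IgG is in SAP 8.6.1. After a normality check on log-scale results, "pairwise comparisons will be performed between treatment groups using Student t-test; Wilcoxon rank sum test will be used if otherwise". SAP 8.6.2 adds that the "Holm-Bonferroni method will be used to control family-wise error rate, both adjusted and unadjusted p-values will be reported".

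On design, SAP 3.2 states that "neither randomization nor blinding will be applicable for this study". SAP 3.1 allows people to be placed in a cohort according to when they can attend for the boost, and has Cohorts 3 and 2 filled before Cohort 1. The schedule of events (SAP 3.3, Table 2) collects Day 1 serum in all three cohorts.

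**The concern.** The SAP's reason for adjusting BT50 applies equally to serum IgG: it is a serum antibody, it is primary, its baseline is measured, and the cohorts are the same. The documents give no reason for treating the two differently.

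Comparing boost schedules is the purpose of the study. For IgG, that comparison rests on a test with no covariate, and the SAP does not say explicitly whether the test uses post-dose values or fold rises. If cohorts differ at Day 1, the two choices can point in opposite directions on the same data. With 10 people per cohort, the plan also gives up precision that a value already collected could supply.

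**Working it through.** The documents give no power, effect size, correlation or IgG variance, so there is no stated figure to reproduce. What follows illustrates the consequence.

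**Inputs from the documents.** Three cohorts of 10 (SAP 5.0); ANCOVA of log post-dose value on cohort and log baseline (SAP 8.6.1.2, Table 4); Holm adjustment over the three cohort pairs (SAP 8.6.2).

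**Assumptions not in the documents.** Natural-log values are bivariate normal with SD 1; the within-cohort baseline/post-dose correlation ρ is 0.3, 0.5, 0.7 or 0.8; the nominal level is 5%; no values lie beyond the assay limits.

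**Step 1: precision, no true baseline difference.** For one pair of cohorts:
- post-dose: variance = 2/10 = 0.2
- fold rise: variance = 0.2 × 2(1−ρ)
- ANCOVA: variance = (1−ρ²)(0.2 + 0.2/25) = 0.2 × 1.04(1−ρ²). Here 25 = 27 − 2, and 27 is the pooled within-cohort degrees of freedom of the baseline.

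The SE ratios are therefore √[1.04(1−ρ²)] against post-dose values and √[1.04(1+ρ)/2] against fold rises.

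If one cohort is offset by 0.5 SD, the expected squared baseline gap is 0.2 + 0.25 = 0.45. The ANCOVA variance becomes (1−ρ²)(0.2 + 0.45/25) = 0.2 × 1.09(1−ρ²), so 1.09 replaces 1.04.

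| SE ratio at ρ = | 0.3 | 0.5 | 0.7 | 0.8 |
|---|---|---|---|---|
| ANCOVA / post-dose, no offset | 0.973 | 0.883 | 0.728 | 0.612 |
| ANCOVA / fold rise, no offset | 0.822 | 0.883 | 0.940 | 0.967 |
| ANCOVA / post-dose, 0.5 SD offset | 0.996 | 0.904 | 0.746 | 0.626 |
| ANCOVA / fold rise, 0.5 SD offset | 0.842 | 0.904 | 0.963 | 0.990 |

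Simulation with 40,000 trials per setting agrees to within 0.005. At ρ = 0 ANCOVA costs about 2% against post-dose values (√1.04 = 1.020).

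**Step 2: bias at a 0.5 SD offset with no schedule effect.** There are two ways the offset could carry forward.
- Case A, all cohorts share one regression on baseline: post-dose ratio exp(0.5ρ); fold-rise ratio exp(−0.5(1−ρ)); ANCOVA 1.
- Case B, the cohort difference is stable from baseline to post-dose: post-dose exp(0.5); fold rise 1; ANCOVA exp(0.5(1−ρ)).

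| Expected ratio at ρ = | 0.3 | 0.5 | 0.7 | 0.8 |
|---|---|---|---|---|
| A: post-dose | 1.16 | 1.28 | 1.42 | 1.49 |
| A: fold rise | 0.70 | 0.78 | 0.86 | 0.90 |
| A: ANCOVA | 1.00 | 1.00 | 1.00 | 1.00 |
| B: post-dose | 1.65 | 1.65 | 1.65 | 1.65 |
| B: fold rise | 1.00 | 1.00 | 1.00 | 1.00 |
| B: ANCOVA | 1.42 | 1.28 | 1.16 | 1.11 |

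The ANCOVA ratio divided by the fold-rise ratio is exp(0.5(1−ρ)) in both cases. Comparing the two estimates therefore cannot show which case holds.

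**Step 3: false positives.** Simulated chance of at least one Holm-significant pair at the same offset:

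| At ρ = | 0.3 | 0.5 | 0.7 | 0.8 |
|---|---|---|---|---|
| A: post-dose | 5.2% | 6.9% | 9.6% | 11.3% |
| A: fold rise | 8.4% | 6.7% | 5.9% | 5.2% |
| A: ANCOVA | 4.2% | 4.1% | 4.4% | 4.3% |
| B: ANCOVA | 9.5% | 7.3% | 5.8% | 5.5% |

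In case B, post-dose values give 15.4% to 15.7% and fold rises 4.3% to 4.5%.

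**Step 4: gaps by chance alone.** The SD of a difference in baseline means is √(2/10) = 0.447, and 0.5/0.447 = 1.118, so a given pair differs by at least 0.5 SD with probability 26%. The largest of the three pairwise gaps reaches 0.5 SD in about 50% of trials.

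**The case against.** The strongest reply is that this is an unpowered Phase 1b study, that SAP 8.6.1 calls for the assays to be summarised descriptively, and that no success rule depends on IgG. The BT50 focus is also consistent: the responder analysis, the ANCOVA and all the added immunogenicity endpoints in SAP 4.2 concern BT50, and Protocol 2.2 names the BT50 rise as the primary immunological endpoint of an earlier study. IgG already has a fold rise with a confidence interval in each cohort. All of this is true and limits the weight of the point. But the SAP does commit to pairwise tests with Holm-adjusted p-values, and a by-cohort fold rise is not a between-cohort contrast.

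A second reply is that ANCOVA can itself be biased without randomisation, as case B shows. That stands, and it is why ANCOVA should not be reported alone.

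A third is that chance gaps are already in the unadjusted test's standard error. That is also correct: with no true offset, the any-pair error is about 4.4% for post-dose values and 4.3% for ANCOVA. The 50% in step 4 shows how often an observed gap will complicate reading the result; it is not an error rate. False positives rise only with a systematic offset, which the documents do not establish.

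Finally, the natural reading of SAP 8.6.1 is that log assay values are tested. If so, one sentence would settle it.

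**Conclusion.** The concern holds, as an improvement that should be made rather than a flaw that invalidates the study. The specific text of SAP 4.2 and 8.6.1.2 limits baseline adjustment to BT50, and Table 4's general wording does not extend it to IgG.

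Across the assumed correlations, ANCOVA is nearer to no effect than post-dose values in both offset cases, and nearer than the fold rise only in case A. It improves precision at every correlation considered, although at ρ = 0.3 with an offset the gain over post-dose values is nil. These sizes rest on the assumed correlation, SD and offset, and on clean data; the SAP's substitution rules for values outside the assay limits were not modelled. Adjusting for baseline IgG does not remove other confounding from how cohorts are filled.

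**What to change.** - In SAP 8.6.1.2, extend the existing model to VP1 serum IgG: log post-dose value, cohort as factor, log Day 1 IgG as covariate. Add the IgG geometric least squares mean and between-cohort ratio, with 95% CIs, to SAP 4.2.
- Report the between-cohort ratio of fold rises with 95% CI beside it as a sensitivity analysis, and say in the CSR whether the two agree. Disagreement would show that the result depends on the baseline assumption, not which estimate is right.
- Apply the SAP 8.6.2 Holm adjustment to the IgG contrasts.
- State in SAP 8.6.1 whether the t-test or Wilcoxon test uses log post-dose values or log fold rises. Leave those tests otherwise unchanged.
- Record the change in SAP 9.0 before database lock.

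The cost is SAP wording, one more model per visit, and three more Holm-adjusted contrasts at 28 days after the second dose. The model uses one degree of freedom and assumes a common slope and roughly normal log residuals. Because SAP 8.6.2 makes no correction across outcomes, the added contrasts should be labelled supportive.

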8.6.2 Multiplicity

There will be multiple outcomes pertaining to immunogenicity; however, each outcome will be analyzed separately, and no corrections will be made to account for multiplicity. Pairwise comparisons among cohorts will also be conducted; Holm-Bonferroni method will be used to control family-wise error rate, both adjusted and unadjusted p-values will be reported.

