4.1. Scientific Rational for Study Design

Emerging evidence generated in clinical settings with the AstraZeneca COVID-19 vaccine (AZD1222) indicates that a 12-week interval between vaccine doses might significantly improve efficacy and immunogenicity of AAV-based vaccination strategies compared to a shorter 4- or 6-week dosing interval (Voysey et al., 2021; Hung and Poland, 2021). In light of these findings, the current Phase 1b study is designed to assess the safety and immunogenicity of the VXA-G1.1-NN vaccine with a 2-dose vaccination schedule using different repeat-dosing intervals (4, 8, or 12 weeks apart) in healthy young adults (18 to 55 years old).

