5.0 Sample Size and Power

No formal sample size calculation was performed for the study. Thirty subjects in total (10 in each cohort) are planned to be enrolled based on experience of a typical Phase I vaccine study.

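### With exactly three cohorts, Shaffer's step-down keeps Holm's family-wise bound, never rejects less, and adds about 2 to 10 points of power to place one boost schedule above both others

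*SAP*

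**What the plan says.** SAP 8.6.2 makes two choices. Across outcomes, "each outcome will be analyzed separately, and no corrections will be made to account for multiplicity". Across cohort pairs, "Holm-Bonferroni method will be used to control family-wise error rate, both adjusted and unadjusted p-values will be reported". It does not define the family to which Holm applies, and it states no alpha.

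The tests that feed this step are in SAP 8.6.1 and 8.6.1.2. On log-scale assay results, if normality is accepted, "pairwise comparisons will be performed between treatment groups using Student t-test; Wilcoxon rank sum test will be used if otherwise". For BT50, the cohorts are compared by baseline-adjusted ANCOVA, with pairwise comparisons 28 days after the second dose; in that model "LSMs for each cohort and differences in LSM between cohorts will be estimated from each model along with 95% CIs".

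On size, SAP 5.0 says: "No formal sample size calculation was performed for the study". It continues: "Thirty subjects in total (10 in each cohort) are planned to be enrolled based on experience of a typical Phase I vaccine study". Three cohorts give three pairs. Neither document states a target difference between schedules or a power.

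**The concern.** Holm compares the ordered p-values with alpha/3, alpha/2 and alpha. The alpha/2 step allows for two true nulls remaining after the first rejection. With three groups that cannot happen: if cohorts A and B differ, cohort C cannot equal both. The stricter second step therefore protects against a configuration that does not exist.

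The second rejection matters in a boost-optimization study, because it separates a schedule that beats one alternative from a schedule that beats both. With 10 subjects per cohort, power for that step is scarce.

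**Working it through.** **1. Error control.** Shaffer's critical values for three groups are alpha/3, alpha, alpha. The possible configurations are:

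- All three cohorts equal: a false rejection needs the smallest p-value to be at most alpha/3, so its probability is at most 3 x alpha/3 = alpha.
- Exactly one pair equal: a false rejection needs that pair's own p-value to be at most alpha, so its probability is at most alpha.
- Exactly two pairs equal: impossible.
- No pair equal: no false rejection is possible.

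The argument needs only valid p-values for each pair. It covers the t-test, the ANCOVA contrasts, and the Wilcoxon test read as a test of equal distributions.

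**2. Where the procedures differ.** At alpha = 0.05 the limits are 0.0167, 0.025, 0.05 for Holm and 0.0167, 0.05, 0.05 for Shaffer. The results differ only when p(1) is at most 0.0167 and p(2) lies above 0.025 and at or below 0.05. The first step is shared, so the chance of at least one rejection is identical.

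**3. Inputs for the size of the gain.** The plan has no power figure to reproduce.

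- n = 10 per cohort (SAP 5.0).
- Two-sided family-wise 0.05: assumed, in line with the 95% intervals.
- Variability: Protocol 9.1 gives an IgA ASC mean of 560 and SD of 740 from a prior study at 10^11 IU. If the response is lognormal, the log-scale SD is sqrt(ln(1 + (740/560)^2)) = sqrt(ln 2.746) = 1.005.
- Differences: assumed two-, three- and four-fold, which are ln 2/1.005 = 0.69, ln 3/1.005 = 1.09 and ln 4/1.005 = 1.38 SD. The only magnitude in the documents is more than two-fold, for another vaccine (Protocol 1.1).
- Family: the three pairs within one outcome at one visit (assumed).

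**4. Probability that the best cohort is significantly above both others.** Two-sample t-tests, 400,000 simulated trials per row (100,000 for the three-fold steady rise):

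| Pattern | Holm | Shaffer | Gain (points) |
|---|---|---|---|
| Two-fold, other two equal | 9.1% | 13.5% | 4.4 |
| Three-fold, other two equal | 34.2% | 43.7% | 9.5 |
| Four-fold, other two equal | 59.8% | 69.5% | 9.7 |
| Steady rise, two-fold overall | 3.6% | 5.7% | 2.1 |
| Steady rise, three-fold overall | 11.2% | 16.5% | 5.3 |
| Steady rise, four-fold overall | 20.5% | 27.9% | 7.4 |

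With the other two cohorts equal, the gain peaks at 10.2 points at 1.25 SD (48.3% to 58.5%). It falls to 2.4 points at 2 SD, where both procedures almost always succeed. For a steady rise it peaks near 8 points.

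**5. Sensitivity, other two cohorts equal.** With a pooled-variance t-test, closer to the ANCOVA, the gains are 4.5, 9.0 and 8.8 points (some differences here are taken before rounding). With Wilcoxon they are about 4, 10 and 12 points. With 8 or 9 subjects per cohort the peak is about 9 points (pooled t).

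**6. Realized family-wise error, Holm and Shaffer.** All cohorts equal: 4.4% and 4.4%. One cohort three-fold higher: 2.9% and 4.5%. One cohort four-fold higher: 3.5% and 4.8%. One cohort far apart: 5.0% and 5.0%. In between, Shaffer uses more of the allowed 5% without exceeding it.

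**The case against.** The strongest reply is that nothing is broken. Holm is standard and valid. The objective is to evaluate immunogenicity, and no criterion requires one schedule to beat both others. The trial is unpowered and non-randomised, and cohorts may be assigned by availability for the boost, so a marginal second rejection would not settle which schedule is best. Unadjusted p-values are reported, so anyone can derive Shaffer-adjusted values later. All of this stands and sets the low priority. What remains is that the SAP has chosen to control family-wise error and report adjusted p-values; prespecifying the sharper method avoids choosing it after the data are seen.

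The variability input is also weak. It comes from one assay at a dose level other than this trial's 10^10 IU, and the baseline-adjusted BT50 analysis was not simulated.

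A reader might also infer that an ordered trend test is missing, since Protocol 4.1 cites evidence from another vaccine that "a 12-week interval between vaccine doses might significantly improve efficacy and immunogenicity". The documents do not support that. For equally spaced intervals of 4, 8 and 12 weeks the linear weights are (4-8, 8-8, 12-8), proportional to (-1, 0, +1). The contrast is therefore week 12 minus week 4, which is already a planned pair with a reported unadjusted p-value. For a three-fold steady rise its power is 65.5%, against 63.9% for the planned unadjusted t-test; for four-fold, 84.5% against 83.2%. The small difference comes from pooling the error term. Adding the contrast uncorrected would raise the chance of any false positive, with all cohorts equal, from 4.4% to 7.3%.

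**Conclusion.** The point holds as an efficiency improvement. For three cohorts Shaffer's procedure has the same strong family-wise bound as Holm and rejects everything Holm rejects. Under the assumptions listed, the gain in the chance of placing one schedule above both others is about 2 to 10 points across two- to four-fold differences.

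Two stronger readings should be resisted. One is that the plan forfeits 10 points outright: that figure is near the top of a curve, needs one cohort three- to four-fold above two equal ones, and no document assumes such an effect. At two-fold the gain is about 4 points, or about 2 for a steady rise, and power is low under either method. The other is that Holm is a mistake: it controls the error as stated.

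**What to change.** In SAP 8.6.2, replace Holm-Bonferroni with Shaffer's procedure and state three things:

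- The family is the three cohort pairs within one outcome at one visit. The limits below hold only for that family.
- Family-wise alpha is given explicitly (0.05 two-sided is assumed here). Ordered p-values are compared with alpha/3, alpha, alpha, stopping at the first non-rejection.
- Adjusted p-values are min(1, 3 x p(1)) for the smallest, then the larger of that value and p(2), then the larger of that result and p(3).

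Keep the unadjusted p-values and do not add a linear-trend contrast. The cost is one or two SAP sentences and a few lines of code, with no extra data and no loss of any rejection that Holm would have made.
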